8.4.2.3 Duration of Response (DOR) using BICR and RECIST 1.1

DOR is defined as the time in months from first objective response (CR or PR) to first occurrence of objective tumor progression (PD according to BICR and RECIST 1.1), or death from any cause, whichever occurs first. Only patients with adequate baseline and post-baseline assessments, in whom a CR or PR is observed will be analyzed for DOR. DOR will be analyzed as a time-to-event endpoint (Section 8.1). DOR will be calculated as: Date of first occurrence of PD - Date of first objective response + 1. See censoring rules in Table 5.1 for more details on the DOR derivation.

8.4.2.4 Time to Response (TTR) using BICR and RECIST 1.1

TTR is defined as the time in months from randomization to first objective response (CR or PR). TTR will only be summarized for patients in whom a CR or PR is assessed. TTR will be calculated as: Date of first objective response - Date of randomization + 1.

TTR will be summarized similar to other continuous variables mentioned in Section 8.1, summary statistics will be provided.

Page 39 of 78 Version: Final v7.0 Date: 05Mar2024

8.4.2.5 Progression Free Survival (PFS) using BICR and RECIST 1.1

PFS is defined as the time in months from randomization to first objective tumor progression (PD according to BICR and RECIST 1.1), or death from any cause, whichever occurs first. PFS will be calculated as: Date of first objective PD or death - Date of randomization + 1.

PFS will be analyzed as a time-to-event endpoint. Patients alive and without disease progression or patients lost to follow-up at data cut-off date will be censored per the censoring rules in Table 5.1.

PFS will be analyzed as a time-to-event endpoint (Section 8.1).

8.4.2.6 ORR, DCR, DOR, TTR, PFS using Investigator assessment and RECIST 1.1

Analysis described in Sections 8.4.1, 8.4.2.1, 8.4.2.2, 8.4.2.3, 8.4.2.4 and 8.4.2.5 will be repeated using Investigator assessment based on RECIST 1.1.

Additionally, a swimmer plot based on RECIST 1.1 for investigator assessment will be presented as described in Section 8.4.1.

8.4.2.7 Overall Survival (OS) for combination arm

OS is defined as the time in months from randomization to death from any cause. OS will be calculated as: Date of death - Date of randomization + 1.

OS will be analyzed using Kaplan-Meier methodology for BNT111 + cemiplimab treatment group. Patients alive or patients lost to follow-up at data cut-off will be censored per the censoring rules in Table 5.2.

8.4.2.8 Health-Related Quality of Life (HRQoL)

Health-Related Quality of Life (HRQoL) will be measured by the European organization for research and treatment of cancer quality-of-Life questionnaire core 30 items (EORTC QLQ-C30) using Patient Global Impression of Severity questionnaire (PGIS) and Patient Global Impression of Change questionnaire (PGIC) for calibration.

Observed and change from baseline values for the global health status score and the functional and symptoms scales for the EORTC QLQ-C30 will be summarized by visit using summary statistics. Score derivation is described in Section 10.6.

Patient Global Impression of Severity questionnaire (PGIS) and Patient Global Impression of Change questionnaire (PGIC) for calibration will be summarized by visit for each treatment group.

8.4.3 Exploratory analyses

Unless otherwise specified the exploratory analyses will be performed for the BNT111 + cemiplimab, BNT111 (mono) and cemiplimab (mono) treatment groups using the CCI set.

Page 40 of 78 Version: Final v7.0 Date: 05Mar2024

8.4.3.1 ORR, DOR, DCR, TTR and PFS using BICR/Investigator assessment and iRECIST

The analysis of endpoints for ORR, DCR, DOR, TTR and PFS described in Sections 8.4.1, 8.4.2.1, 8.4.2.2, 8.4.2.3, 8.4.2.4, 8.4.2.5 and 8.4.2.6 will be repeated for both the BICR and Investigator assessments using response based on the iRECIST guidelines. It is noted that, per the iRECIST guidelines, first occurrence of objective tumor progression is the date that progression criteria are met (i.e. the date of iUPD) provided that iCPD is confirmed at the next assessment and iSD (or Non-iCR/Non-iUPD for BICR data), iPR or iCR had not occurred before iCPD. Further details can be seen in the iRECIST guidelines.

Additionally, a swimmer plot based on iRECIST for BICR and investigator assessment will be presented as described in Sections 8.4.1.

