5.1.3 Inclusion criteria for entering add-on therapy

- 1. Patients must have confirmed disease progression on monotherapy in Arm 2 or 3 of the trial.
 - a. An initial radiological progression needs to be verified by BICR.
 - Radiological progression to be confirmed by two scans 4 to 12 wks apart unless initial progression is accompanied by new symptoms, or deterioration of PS not attributed to toxicity, in which case one scan is sufficient.
- 2. Patients must sign a new ICF to continue with add-on therapy. Informed consent must be documented before any add-on-specific procedure is performed.
- 3. WOCBP must have a negative serum (beta-hCG) at baseline. Patients that are post-menopausal or permanently sterilized can be considered as not having reproductive potential. For a definition of WOCBP, see Section 10.4.
- 4. Female patients of reproductive potential must agree to use adequate contraception during and for 6 months after the last trial drug administration (Section 10.4).
- 5. WOCBP must agree not to donate eggs (ova, oocytes) for the purposes of assisted reproduction during trial starting at screening, during the trial and for 6 months after receiving the last trial treatment.
- 6. A man who is sexually active with a WOCBP and has not had a vasectomy must agree to use a barrier method of birth control, e.g., either condom with spermicidal foam/gel/film/cream/suppository or partner with occlusive cap (diaphragm or cervical/vault caps) with spermicidal foam/gel/film/cream/suppository, and all men must also not donate sperm during the trial and for 6 months after receiving the last trial treatment. For a definition of adequate contraception, see Section 10.4.

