8.1.2 Tumor evaluations

At screening and during treatment

Patients will undergo regular CT or MRI imaging (include chest, abdomen and pelvis and other locations with tumor involvement) assessments of tumors from screening and

BioNTech SE Confidential

Clinical Trial Protocol BNT111-01

Page 77 of 133 Version: 7.0 Date: 09 FEB 2023

throughout the trial. Skin lesions can be followed by photography. At screening, preferably an MRI scan should be done to assess presence of brain metastasis (for patients with a contra-indication for MRI, a contrast-enhanced CT scan is allowed). If a patient has brain metastasis, stability of the lesions should be confirmed and lesions should be followed at each tumor assessment.

All measurable and evaluable lesions should be assessed at screening and target as well as non-target lesions identified and documented following RECIST 1.1 criteria. Tumor assessments, including brain imaging, performed as standard of care prior to obtaining informed consent and within 28 days prior to randomization do not have to be repeated at screening.

Tumor response will be assessed every 6 (± 1) wks for the first 3 months, then every 9 (± 1) wks for the next 9 months and every 12 (± 2) wks thereafter, regardless of dose delays, until (confirmed) disease progression, death, withdrawal of consent, or until the start of next-line anti-cancer therapy, whichever occurs earlier (Section 1.3).

Lesion photography should be performed for cutaneous or palpable lesions at the required tumor assessment time points. When possible, the same individual should photograph and measure the lesions for a given patient to decrease intra-patient variability.

Radiological progression should be confirmed by two scans 4 to 12 wks apart. If progression is accompanied by new symptoms or deterioration of PS not attributed to toxicity one scan is sufficient.

Tumor responses will be measured by RECIST 1.1 / iRECIST and are to continue according to the schedule in patients who undergo complete trial treatment and in patients who discontinue treatment for reasons other than disease progression, consent withdrawal, or patient's withdrawal from the trial.

The same radiographic procedure used to assess disease sites at screening should be used for subsequent tumor assessments (e.g., the same protocol for CT scan). An extra scan should be scheduled if clinically indicated.

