The Safety set will be used for all safety analyses. The Add-on Treatment set will be used for analysis of both safety and efficacy data. Patients randomized to monotherapy (arm 2 and arm 3) who enter add-on treatment period are included in the analysis using both the mITT set, ITT set and the Add-on Treatment set, unless specified otherwise.

The following will occur for the analysis of ORR, DCR, DOR, TTR, PFS, OS, DEoR and EORTC endpoints and for the exploratory analysis of Duration of Disease Control (DDC):

- Tumor response endpoints ORR, DCR, DOR, DDC, TTR, DEoR and PFS: for the analysis using the set or set (sensitivity analysis for ORR (including DCR)), only the data until the day before first dose of add-on treatment will be used. For the analysis using the Add-on Treatment set, only the data from date of first dose of add-on treatment will be used.
- OS: for analysis using the set and Add-on Treatment set, all data would be used. For the exploratory analysis using the Add-on Treatment set (BNT111 + add-on cemiplimab and cemiplimab + add-on BNT111 treatment groups) the data from first day of add-on treatment would be used.
- For EORTC endpoints (Section 8.4.2.8) the summaries/analyzes will be performed as follows:
 - (i) While using set, data until the day before first dose of add-on treatment would be used.
 - (ii) In addition, a separate summary from first dose of add-on treatment to EOS, for the Add-on Treatment set.

All safety analyses will be based on the treatment actually received by the patient ('as treated'). All other analyses will be based on the treatment the patient was randomized to ('as randomized'), unless stated otherwise.

The following will occur for the analysis of safety data (apart from Adverse events)

- For the analysis of safety data using the Safety set, only data until the day before first dose of add-on treatment, if there is add-on treatment, or all data if there is no add-on treatment will be used.
- For the analysis of safety data using the Add-on Treatment set, only data from date of first dose of add-on treatment will be used.

The primary analysis of the trial will be performed based on all available data from a clinical data cut-off that will occur when all patients are randomized and response evaluable (i.e., having at least 3 post-baseline tumor assessments or discontinued before).

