10.5 Appendix 5: Censoring rules

Table 5.1 Censoring Rules for PFS, DOR & DDC Based on Food & Drug Administration (FDA) Guidelines

For calculation of 2 or more missed consecutive scheduled assessments, see the text after the censoring rules tables.

If a subject met multiple censoring criteria, the earliest censoring date will be used.

Situation (Censoring Order)	Date Patient Has Event or is Censored	Situation Outcome
Inadequate baseline assessment* (1)	Randomization date	Censored
Inadequate post-baseline assessments* (2)	Randomization date	Censored
* Not applicable to DOR and DCR		
Progression documented on or between scheduled tumor assessments	Date of first objective tumor assessment showing objective progression	Progressed (Event)
Progression documented not after 2 or more missed consecutive scheduled assessments during the treatment period or not after 1 or more missed scheduled assessments during the Follow-up period	For RECIST 1.1, the Date of objective progression / for iRECIST, the date of iUPD if progression associated with that iUPD has been confirmed.	Progressed (Event)
Death (and progression has not occurred previously) not after 2 or more missed consecutive scheduled assessments during the treatment period or not after 1 or more missed scheduled assessments during the Follow-up period	Date of death	Death (Event)

Statistical Analysis Plan (SAP) BNT111-01

Page 71 of 78 Version: Final v7.0 Date: 05Mar2024

Situation (Censoring Order)	Date Patient Has Event or is Censored	Situation Outcome
Death without objective progression	Date of death	Death (Event)
Death or progression after 2 or more consecutive missing scheduled assessments during the treatment period or after 1 or more missed scheduled assessments during the Follow-up period (3)	Date of last adequate assessment with evidence of no progression; if no adequate assessment exists then censored at the randomization date.	Censored
New anti-cancer therapy started prior to progression or death (4)	Date of last adequate assessment with evidence of no progression before anti-cancer therapy; if no adequate assessment exists then censored at the randomization date	Censored
No progression or death (6)	Date of last adequate assessment with evidence of no progression; if no adequate assessment exists then censored at the randomization date	Censored

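### The iRECIST rule counts progression only when confirmed, but the protocol accepts one scan with symptoms, so an iUPD with no later scan is mostly censored in the exploratory iRECIST PFS, DOR and DDC

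*SAP*

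**What the plan says.** **When iRECIST progression is an event.** SAP 8.4.3.1 uses the iUPD date, "i.e. the date of iUPD) provided that iCPD is confirmed at the next assessment". SAP Appendix 5, Table 5.1 has the matching line, "for iRECIST, the date of iUPD if progression associated with that iUPD has been confirmed". SAP 8.4.3.3 carries the iRECIST analysis over to duration of disease control (DDC).

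**When the protocol requires a second scan.** Protocol 8.1.2 asks for two scans 4 to 12 weeks apart, but adds: "If progression is accompanied by new symptoms or deterioration of PS not attributed to toxicity one scan is sufficient". Scheduled assessments run "until (confirmed) disease progression, death, withdrawal of consent, or until the start of next-line anti-cancer therapy, whichever occurs earlier". Protocol 4.1.5 continues efficacy assessments only for patients whose last on-treatment assessment was CR, PR or SD, and stops them at PD.

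**Add-on entry in Arms 2 and 3.** Protocol 5.1.3 repeats the exception for symptomatic progression, "in which case one scan is sufficient". For the randomized-period tumor endpoints, SAP 8.1 states that "only the data until the day before first dose of add-on treatment will be used".

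**Deaths.** Table 5.1 lists "Death without objective progression" as an event with no limit on missed scans. Situation 3 of the same table censors a death that follows two missed scans on treatment or one in follow-up.

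**The concern.** The SAP makes the event depend on a scan that the protocol does not require from patients whose progression is symptomatic. Table 5.1 has no line for an iUPD that is never re-imaged, so these patients fall to the censoring lines. They have just progressed on imaging and are clinically worse, so their censoring is related to outcome, whereas Kaplan-Meier estimation assumes that it is not.

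At stake is how the iRECIST results are read. Under RECIST 1.1 the analysis needs no confirmation of progression, so these patients are events there. Part of any gap between the iRECIST and RECIST 1.1 curves would then reflect missing second scans and not pseudoprogression. Only Arms 2 and 3 have the add-on route, so the distortion may differ between the combination and the calibrator arms.

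**Working it through.** The documents give no event count or assumption for iRECIST PFS, DOR or DDC, so there is no planned figure to reproduce. The check has two parts.

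**1. Paths through Table 5.1 for a patient with one symptomatic iUPD scan and none after it**

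| What happens next | Situation | Result |
|---|---|---|
| Nothing further by data cut-off | 6 | Censored at last progression-free assessment |
| New anti-cancer therapy | 4 | Censored at last progression-free assessment before it |
| Stops for a reason recorded as clinical progression | 5 | Censored at last tumor assessment before stopping |
| Death after a missed follow-up scan | 3 | Censored at last progression-free assessment |
| Death before a scan counts as missed | death lines | Event, dated at death and not at iUPD |
| Add-on entry (Arms 2 and 3) | none of its own | Later scans not used; falls to the lines above |

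Where several lines apply, Table 5.1 takes the earliest censoring date. If no progression-free assessment exists, PFS is censored at randomization.

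The SAP's limits for one missed scan are 6×7+7+7 = 56 days (first 3 months), 9×7+7+7 = 77 days (next 9 months) and 12×7+14+14 = 112 days thereafter.

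**2. Size, as an illustration**

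From the documents: scans at weeks 6, 12, 21, 30, 39 and 48. Assumed, because the documents do not say: exponential progression with a 5-month median; a share f of progressors, at random, with one scan only; all of these censored at the preceding scan. That last assumption makes this the upper case.

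Let r be the true probability of remaining progression-free over one scan interval. Of those progression-free at the previous scan, the risk set is 1 − f(1 − r) and the events are (1 − f)(1 − r). The Kaplan-Meier factor is therefore r / [1 − f(1 − r)].

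- Hazard = ln 2 / (5 × 30.4375/7 weeks) = 0.03188 per week.
- 6-week interval: r = 0.8259. 9-week interval: r = 0.7506.
- Week 30 (two intervals of each length), f = 0: 0.8259² × 0.7506² = 0.384.
- Week 30, f = 0.2: 0.384 / [(1 − 0.2×0.1741)² × (1 − 0.2×0.2494)²] = 0.384 / 0.841 = 0.457.

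| Single-scan share f | 30-week PFS | 48-week PFS |
|---|---|---|
| 0% | 38.4% | 21.6% |
| 10% | 41.9% | 24.8% |
| 20% | 45.7% | 28.5% |
| 30% | 50.0% | 32.9% |

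**Allowing for deaths.** A simulation of 40,000 patients used a 3-month median and counted a death within the one-missed-scan limit as an event. Median survival after progression was set at 3, 6 or 12 months. The share of single-scan patients censored was 56–57%, 74–75% and 86–87% respectively. The last column applies the formula above to the same 3-month median at week 21, the last scan before 6 months.

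| f | 6-month PFS, deaths allowed for | All censored |
|---|---|---|
| 0% | 32.7% | 32.8% |
| 10% | 34.8–35.8% | 36.0% |
| 20% | 37.1–39.0% | 39.7% |
| 30% | 39.9–42.2% | 43.9% |

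The direction is unchanged and the rise is smaller. New therapy and add-on entry were not modelled; both would raise the censored share. The Kaplan-Meier median did not move in the simulation (4.83 months at every f), because events fall on scan dates. In the 5-month closed form it also stays at week 30, although at f = 30% the curve there is only just below one half.

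**The case against.** **The rule may be settled elsewhere.** SAP 8.4.3.1 refers to the iRECIST guidelines, and SAP 8.1 to a separate programming guideline for deriving iRECIST data. Neither is available here, and either might cover an iUPD with no later scan. That stands as a caveat. It does not change the SAP text, and Table 5.1 is where the censoring rules are set.

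**Table 5.1 is looser than 8.4.3.1.** It requires "the date of iUPD if progression associated with that iUPD has been confirmed" without naming iCPD or the next assessment, and the protocol's idea of confirmed progression includes the symptomatic one-scan route. That reading is possible, but it would set the table against 8.4.3.1, so the text needs settling either way.

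**Confirmation is what separates iRECIST from RECIST 1.1.** Counting unconfirmed iUPDs moves the two analyses closer together. This is fair, and it is why the confirmed-only rule should be kept as a sensitivity analysis.

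**Stronger readings that the documents do not support.**

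- A reader might infer that these patients can never reach iCPD. One scan is sufficient under the protocol, but a second is not forbidden. Protocol 6.3 allows treatment through initial radiological progression, and 8.1.2 allows an extra scan if clinically indicated.
- A reader might infer that the sickest patients are all censored. Those who die soon after the scan are events, although dated late.
- A reader might infer that the true bias exceeds the figures above because symptomatic patients progress earlier. No passage supports that premise, and the direction depends on the time point. When the single-scan cases in the 5-month model were assigned to the earliest progressors, 20% gave 48.0% at week 30 (against 45.7% at random) but 27.0% at week 48 (against 28.4% at random in the same simulation).

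**Conclusion.** The gap is real and minor. Followed as written, the SAP mostly censors patients who have an iUPD and no later evaluable scan, and it does so because of how the protocol handles symptomatic progression. The resulting bias in iRECIST PFS, DOR and DDC is upward, possibly more so in Arms 2 and 3.

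The size cannot be fixed from the documents. With an assumed single-scan share of 10–30%, the rise in 30-week PFS is about 3 to 12 percentage points in the upper case (5-month median, all censored). Allowing for deaths, the rise in 6-month PFS is about 2 to 10 points (3-month median). The two sets rest on different medians and time points.

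The consequence is limited. The iRECIST endpoints are exploratory, and no formal comparison between arms is planned. The primary ORR and the RECIST 1.1 PFS and DOR do not depend on this rule.

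**What to change.** 1. In SAP 8.4.3.1 and Table 5.1, count an iUPD with no later evaluable scan in the analysis period as an event at the iUPD date. Name the cases: single-scan symptomatic progression, stopping for progression, add-on entry, and death. Make the same change in the iRECIST programming guideline if it does not already do this.
2. Keep the confirmed-only rule as a sensitivity analysis.
3. Report the number of such patients by arm.
4. Reconcile the Table 5.1 line "Death without objective progression" (an event with no missed-scan limit) with situation 3 (death after missed scans, censored). Which of the two prevails decides how many of these patients are censored.

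The cost is one sentence in 8.4.3.1, one line in Table 5.1, a clarification of the death lines, and one extra run of the iRECIST time-to-event programs. Trial conduct, data collection and the RECIST 1.1 event definition do not change. Item 4 also touches the RECIST 1.1 analyses, because they share Table 5.1, but only by removing an ambiguity.

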8.4.3.2 Duration of Disease Control (DDC) using BICR/Investigator assessment and RECIST 1.1

DDC is defined as the time in months from first objective response (CR or PR or SD (for BICR data, the Non-CR/Non-PD response will be included in the DDC, similarly to SD response) (SD assessed at least 6 weeks [+/- 1 wk] after first dose)) to first occurrence of objective tumor progression (PD according to BICR and RECIST 1.1), or death from any cause, whichever occurs first. Only patients in whom a CR or PR or SD (or Non-CR/Non-PD for BICR data) (SD assessed at least 6 weeks [+/- 1 wk] after first dose) is observed will be analyzed for DDC. DDC will be analyzed as a time-to-event endpoint (Section 8.1) based on SD observed as best overall response). DDC will be calculated as: Date of first occurrence of PD - Date of first objective response + 1. DOR will be calculated as: Date of first occurrence of PD - Date of first objective response + 1. See censoring rules in Table 5.1 for more details on the DDC derivation.

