8.4.3.3 Duration of Disease Control (DDC) using BICR/Investigator assessment and iRECIST 1.1

The analysis of endpoint for DDC described in Section 8.4.3.2 will be repeated for both the BICR and Investigator assessments using response based on the iRECIST guidelines.

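### SAP 8.4.3.2 contradicts itself on duration of disease control: it covers both assessors but names only BICR progression as the end event, and a stable-disease clause conflicts with its own definition

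*SAP*

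**What the plan says.** SAP 8.4.3.2 is headed "Duration of Disease Control (DDC) using BICR/Investigator assessment and RECIST 1.1", so one section serves both assessors. Its rules are:

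- **Start:** "DDC is defined as the time in months from first objective response (CR or PR or SD", with SD counted only from about week 6 and BICR Non-CR/Non-PD treated like SD.
- **End:** "first occurrence of objective tumor progression (PD according to BICR and RECIST 1.1), or death from any cause, whichever occurs first".
- **Who is analyzed:** "Only patients in whom a CR or PR or SD (or Non-CR/Non-PD for BICR data" is observed.
- **Analysis:** "DDC will be analyzed as a time-to-event endpoint (Section 8.1) based on SD observed as best overall response", followed by a closing parenthesis that has no partner.
- **Formula:** "DDC will be calculated as: Date of first occurrence of PD - Date of first objective response + 1". The next sentence reads "DOR will be calculated as: Date of first occurrence of PD - Date of first objective response + 1".

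Section 8.4.3.3 adds that the DDC analysis "will be repeated for both the BICR and Investigator assessments using response based on the iRECIST guidelines". Section 5.2 lists DDC among the IA2 outputs for both assessors under both sets of criteria. SAP Appendix 1 records DDC as an exploratory analysis that the protocol does not contain.

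**The concern.** Two rules that a programmer needs are not settled: which event ends DDC, and which response starts it.

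On the end event, ORR, DCR, DOR, TTR and PFS are first defined for BICR. Section 8.4.2.6 then repeats them for the investigator, and 8.4.3.1 repeats them for iRECIST. DDC is in neither list. Its own section names both assessors in the title and only BICR in the event. Followed to the letter, investigator DDC begins at an investigator-assessed response and ends at a BICR-assessed progression.

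This could affect real patients. Under Protocol 8.1.2 and 8.1.3 the investigator makes the treatment decisions, and BICR reads are not shared with sites except to verify progression before add-on therapy. A patient with investigator progression may start new therapy before BICR calls progression. On the literal rule, Table 5.1 would then censor that patient in the investigator analysis, although the investigator recorded an event.

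On the start, the SD clause sits beside a definition and a population sentence that both name CR, PR and SD. It can be read as limiting the analysis to patients whose best response is SD, or as letting SD start the clock only when nothing better follows.

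**Working it through.** The documents give no design figure for DDC, so there is none to reproduce. The check compares the texts, then sizes the two ambiguities.

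**Texts side by side**

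| Item | SAP 8.4.3.2 | Elsewhere in the SAP |
|---|---|---|
| Assessor of the end event | BICR, RECIST 1.1 only | 8.4.2.3 and 8.4.2.5 also name BICR only, but 8.4.2.6 repeats them for the investigator. DDC is not in that list |
| Criteria | RECIST 1.1 | 8.4.3.3 moves to iRECIST for both assessors without restating the event |
| Start | First CR, PR or SD in the definition; first objective response in the formula | 8.4.2.3 and 8.4.2.4 limit that term to CR or PR. Table 5.1 refers to objective response for DOR and to disease control for DDC |
| Population | CR, PR or SD, then a clause about SD as best response | 8.4.2.2 (DCR) counts CR, PR or SD as best response |
| Death | In the definition, not in the formula | Table 5.1 lists death as an event |

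**Size**

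Inputs: target days from SAP Appendix 7 (week 6 = 43, week 12 = 85, week 21 = 148, week 39 = 274), and 30.4375 days per month from SAP 8.1. Appendix 7 serves the depth-of-response analysis, so its days are used here only as nominal scan dates. The patient courses are assumed.

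Formula: DDC = end day − start day + 1.

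*Assessor of the end event.* SD at week 6, investigator PD at week 12, BICR PD at week 21:

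- ending at investigator PD: 85 − 43 + 1 = 43 days (1.41 months)
- ending at BICR PD: 148 − 43 + 1 = 106 days (3.48 months)
- difference: 63 days (2.07 months)

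If BICR calls PD at week 12 and the investigator at week 21, the two values swap, and the literal rule gives the shorter one.

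*Start.* SD at weeks 6 and 12, PR at week 21, PD at week 39:

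- from first SD: 274 − 43 + 1 = 232 days (7.62 months)
- from PR: 274 − 148 + 1 = 127 days (4.17 months)
- difference: 105 days (3.45 months)

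If the PR comes at week 12, the start moves by 85 − 43 = 42 days (1.38 months).

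**The case against.** The strongest reply is that this is loose drafting and the intent is recoverable. The section title names both assessors, and the qualifiers for BICR data make sense only if each assessor has its own analysis. The end event looks like wording carried over from DOR. Table 5.1, which the section cites for the derivation, describes progression without naming an assessor, gives the iUPD date for iRECIST, and includes death. A RECIST 1.1 event cannot carry over to 8.4.3.3 unchanged, so the gap is clearest for investigator DDC under RECIST 1.1. The SD clause may simply echo the DCR definition, meaning that SD patients qualify through best overall response. Scanning also need not stop at the investigator's first PD, because Protocol 8.1.2 asks for confirmation by a second scan 4 to 12 weeks later unless symptoms or performance status worsen.

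Much of this stands as evidence of intent. It does not supply the missing sentence on the assessor, and it does not remove a clause that contradicts the two sentences before it.

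Two stronger readings are tempting. A reader might infer that responders are dropped or start late. The documents do not support that as the plan: the paragraph expressly includes CR and PR patients, and Table 5.1 ties DDC to disease control. A reader might also infer that investigator DDC is systematically too long. That is not supported either, because the direction depends on which assessor calls progression first and the documents give no discordance rate.

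**Conclusion.** Wrong as written, with low impact. Section 8.4.3.2 is inconsistent on the end event and on the role of SD, and its formula omits death. Two programmers following it could produce different DDC values for the same patient.

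The differences of 63 days (end date, either direction) and 105 days (start date) hold for individual patients with the assumed courses and on-schedule scans. The effect on a median cannot be estimated from the documents, which give neither discordance between assessors nor the timing of responses.

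DDC is exploratory, untested and absent from the protocol. The primary ORR analysis does not depend on it.

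**What to change.** Replace the conflicting text in 8.4.3.2 with two sentences to this effect:

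1. DDC is analyzed in all patients with disease control, from the first qualifying CR, PR or SD (or Non-CR/Non-PD for BICR), whichever is earliest.
2. It ends at first progression by the same assessor and the same criteria (RECIST 1.1 here, iRECIST in 8.4.3.3) or at death, and is calculated as date of first progression or death minus date of first qualifying response plus 1.

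Delete the clause on SD as best overall response and the DOR formula. In the same edit, check the Table 5.1 footnote, which refers to DOR and DCR in a table headed PFS, DOR and DDC.

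The cost is a short SAP edit with no change to design, data collection or sample size. Programming stays the same if it already uses assessor-specific progression and starts at first disease control. If DDC output has already been produced, record which rule was programmed.
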